1.2 Study objectives and endpoints

The study objectives and endpoints are presented in the following table.

Table 1-1 Objectives and endpoints

Objective	Endpoint
Primary	
Assess the efficacy of deferasirox in liver iron removal after 52 weeks of treatment	Change in LIC from baseline after 52 weeks of treatment
Secondary	
Assess response rates in subset of patients with baseline LIC > 15 mg Fe/g dw	Proportion of patients with baseline LIC > 15 achieving LIC < 5 mg Fe/g dw and time to achieving LIC < 5 mg Fe/g dw
Assess long-term efficacy of treatment to a target LIC of 3 mg Fe/g dw	Time from target LIC of 3 mg Fe/g dw to the first LIC \geq 5 mg Fe/g dw in the follow up period
Evaluate the impact of deferasirox on adult QoL	Change in health-related outcomes using Medical Outcomes Study Form 36 (SF-36v2)
Evaluate the impact of deferasirox on pediatric QoL	Change in health-related outcomes using the Pediatric Quality of Life questionnaire (PedsQL™)

Evaluate the efficacy of deferasirox in liver iron removal	Change in LIC from baseline
Assess the correlation of change in SF and LIC	SF vs LIC at baseline and EOS
Confirm the efficacy of deferasirox in liver iron removal in NTDT syndrome	Change in LIC from baseline after 52 weeks of treatment by underlying NTDT syndrome
Assess the efficacy of deferasirox in decreasing SF after 52 weeks of treatment	Change in SF from baseline after 52 weeks of treatment
Evaluate the safety of deferasirox doses up to 30 mg/kg/day dose	Safety parameters, labs, adverse events (AEs)
Assess the efficacy of Deferasirox in endocrine function	Change from baseline during treatment period in total and free testosterone (males), LH and FSH (females), TSH, total and free T4, total and free T3, fasting plasma glucose, insulin, insulin resistance, and cortisol.
Conduct PK analysis in a subgroup of patients	PK parameters (AUC, Cmax, Tmax and trough levels) during the study period
Safety	
All safety objectives will be performed.	All safety events and assessments will be included
[REDACTED]	

2 Statistical methods

2.1 Data analysis general information

Data will be analyzed by Novartis according to the data analysis section 10 of the study protocol and its amendments.

All analyses will be performed by using SAS Version 9.2 or higher.

As described in Section 10 of the protocol, in addition to the overall population analysis, statistical analysis will be performed according to ethnicity groups: Chinese/non-Chinese patients.

All summaries described below will be performed by ethnicity group and all patients, if not otherwise stated.

2.1.1 General definitions

Observation periods for safety analysis

The overall observation period will be divided into three mutually exclusive segments:

1. pre-treatment period: from day of patient's informed consent to the day before first dose of study medication
2. on-treatment period: from day of first dose of study medication to 30 days after last nonzero dose of study medication.
3. post-treatment period: starting at day 30+1 after last dose of study medication.

Safety summaries (tables, figures) include only data that from the pre-treatment period (to display the baseline status e.g. for ECG) and the on-treatment period, i.e. no data from the post-treatment period must be included if not otherwise requested from Health Authorities. In particular, summary tables for adverse events (AEs) have to include only AEs that started or worsened during the on-treatment period, the so-called treatment-emergent AEs. Similarly, summary tables and figures only include lab values observed during the on-treatment period. However, all safety data (including those from the post-treatment period) will be listed and those collected during the pre-treatment and post-treatment period will be flagged.

The above defined observation periods will be only applicable for safety analysis. In particular, all post-baseline values will be used in the analyses of LIC, serum ferritin [REDACTED] defined in the protocol section 7.2.1 for efficacy assessment.

Study day, last assessment day and baseline

Study day

Since this is an open label study, for all variables (safety or efficacy), study day will be defined as the number of days since the date of first dose of study medication. For a particular date on or after first dose, it is calculated as:

Study day = Assessment date – Date of first dose of study medication + 1.

Therefore, the date of the first dose of study medication will be Day 1 by definition.

The day before this day will be defined to be Day -1, i.e., there is no Day 0. Study days before first dose of study medication will be calculated as:

Study day = Assessment date – Date of first dose of study medication.

In the above study day calculation, the date of the first day of study drug will be replaced with the study drug assignment date if the patient doesn't take any study drug.

So if the patient doesn't take the study drug, Day 1 is the study drug assignment date.

Definition of baseline value

For all variables, the baseline value will be defined to be the last available value prior to or on Day 1.

For serum ferritin the baseline value will be calculated from the mean of values measured prior to or on Day 1.

Last assessment day

For the safety assessment, the censoring date will be the last treatment date+30 days. For example, time to first specific adverse event will be censored at the last treatment date+30 days for a patient without the specified adverse event on-treatment.

End of treatment year 1

All data collected at Week 52 visit will be noted as End of treatment year 1

Month definition

Unless otherwise noted (e.g. for the calculation for month of exposure, 1 month = 365.25/12 days), one month will be defined as 30 days, with the exception of month 1 which consisted the first 45 days. When multiple values will be present for a month, the average value will be used unless otherwise noted. The grouping of each month will be according to the following rules:

- If the day is in (1, 30+15] assign to month 1.
- If the day is in (30*x-15, 30*x+15] assign to month x<12.
- If the day is in (345, 378] assign to month 12.

This would allow for a +/- 15 days window for each month.

Quarter definition

Unless otherwise noted, the quarter is defined as shown in the table below:

Visit Description	First day in window	Scheduled day in window	Last day in window	Quarter
Baseline	-35		1	
Week 2	2	14	21	1
Week 4	22	28	42	1
Week 8	43	56	70	1
Week 12	71	84	98	1
Week 16	99	112	126	2
Week 20	127	140	154	2
Week 24	155	168	182	2
Week 28	183	196	210	3
Week 32	211	224	238	3
Week 36	239	252	266	3
Week 40	267	280	294	4

Visit Description	First day in window	Scheduled day in window	Last day in window	Quarter
Week 44	295	308	322	4
Week 48	323	336	350	4
Week 52	351	364	378	4
Week 56	379	392	406	5
Week 60	407	420	434	5
Week 64	435	448	462	5
Week 68	463	476	490	6
Week 72	491	504	518	6
Week 76	519	532	546	6
Week 80	547	560	574	7
Week 84	575	588	602	7
Week 88	603	616	630	7
Week 92	631	644	658	8
Week 96	659	672	686	8
Week 100	687	700	714	8
Week 104	715	728	742	8
Week 108	743	756	770	9
Week 112	771	784	798	9
Week 116	799	812	826	9
Week 120	827	840	854	10
Week 124	855	868	882	10
Week 128	883	896	910	10
Week 132	911	924	938	11
Week 136	939	952	966	11
Week 140	967	980	994	11
Week 144	995	1008	1022	12
Week 148	1023	1036	1050	12
Week 152	1051	1064	1078	12
Week 156	1079	1092	1106	12

Visit Description	First day in window	Scheduled day in window	Last day in window	Quarter
Week 160	1107	1120	1134	13
Week 164	1135	1148	1162	13
Week 168	1163	1176	1190	13
Week 172	1191	1204	1218	14
Week 176	1219	1232	1246	14
Week 180	1247	1260	1274	14
Week 184	1275	1288	1302	15
Week 188	1303	1316	1330	15
Week 192	1331	1344	1358	15
Week 196	1359	1372	1386	16
Week 200	1387	1400	1414	16
Week 204	1415	1428	1442	16
Week 208	1443	1456	1470	16
Week 212	1471	1484	1498	17
Week 216	1499	1512	1526	17
Week 220	1527	1540	1554	17
Week 224	1555	1568	1582	18
Week 228	1583	1596	1610	18
Week 232	1611	1624	1638	18
Week 236	1639	1652	1666	19
Week 240	1667	1680	1694	19
Week 244	1695	1708	1722	19
Week 248	1723	1736	1750	20
Week 252	1751	1764	1778	20
Week 256	1779	1792	1806	20
Week 260	1807	1820	1834	20

2.2 Analysis sets

The **Full Analysis Set (FAS)** consists of all patients who will be assigned at least one dose of study drug. The FAS will be used for all efficacy analyses.

The **Safety Set** consists of all patients who will receive at least one dose of study drug.

The **pharmacokinetic analysis set (PAS)** consists of all patients from FAS set who have evaluable pharmacokinetic (PK) data.

The **Ethnicity group**: The Patients will be grouped based on the ethnicity as Chinese patients, non-Chinese patients and all patients.

2.2.1 Subgroup of interest

The following subgroups will be considered for further analyses:

- Age categories (<18 years and \geq 18 years)
- Baseline LIC categories (\leq 7, $>$ 7 - 15 and $>$ 15 mg Fe/g dw)
- NTDT diagnosis subtypes (Beta-thalassemia intermedia, HbE Beta-thalassemia, Alpha-thalassemia intermedia (HbH disease) and Other)
- Average actual daily dose ($>$ 0 - $<$ 7.5, 7.5 - 12.5, $>$ 12.5 - 17.5 and $>$ 17.5 mg/kg/day)

2.3 Patient disposition, demographics and other baseline characteristics

Demographic and baseline characteristics will be summarized by ethnicity group and overall for the FAS.

Demographics include age, age group (<18 years, 18-<50 years, 50-<65 years, \geq 65 years), gender, race. Other baseline characteristics include weight, weight group ($<$ 35 kg, 35-<55 kg, 55-<75 kg, \geq 75 kg), main underlying disease, history of blood transfusion (Yes/No), history of splenectomy (Yes/No), history of chelation therapy (Yes/No), type of last chelation therapy prior to the study, hepatitis B and C status, medical history by MedDRA primary SOC and preferred term, clinically significant abnormality in baseline ECG (Yes/No), abnormality in baseline audiometric test (Yes/No) and (clinically significant/non-significant), abnormality in baseline ocular exam (Yes/No) and (clinically significant/non-significant), baseline LIC, baseline LIC group ($<$ 5, 5- \leq 7, $>$ 7-15, $>$ 15 mg Fe/g dw), baseline serum ferritin, baseline serum ferritin group ($<$ 300, \geq 300-500, $>$ 500-1000, $>$ 1000-2500, $>$ 2500-5000, $>$ 5000 ng/mL), baseline creatinine, baseline creatinine group (\leq upper limit of normal range (ULN), $>$ ULN), baseline creatinine clearance, baseline creatinine clearance group ($<$ 60, 60-<90, 90-<160, \geq 160 mL/min), baseline ALT, baseline ALT group (\leq ULN, $>$ ULN- $5 \times$ ULN, $>$ 5 \times ULN), baseline AST, baseline AST group (\leq ULN, $>$ ULN- $5 \times$ ULN, $>$ 5 \times ULN), urine protein/creatinine ratio (\leq 0.2 mg/mg, $>$ 0.2-1 mg/mg, $>$ 1 mg/mg).

2.4 Treatments (study treatment, rescue medication, concomitant therapies, compliance)

2.4.1 Study treatment / compliance

The duration of exposure is defined as the number of months between the start and end of study medication. One month of exposure corresponded to 365.25/12 days. So the duration of exposure in month will be calculated as (study medication end date-study medication start date+1)/30.4375.

The following variables will be summarized for the Safety Set : duration of exposure, in months and in categories (<3 months, 3-<6 months, 6-<9 months, and so on); average planned (mg/kg/day) and average actual daily dose (>0 -<7.5, 7.5 - 12.5, >12.5 - 17.5 and >17.5 mg/kg/day); cumulative planned (mg/kg) and actually administered dose (mg/kg); percentage of planned dose taken (as calculated from DAR); number, mean length, and total length of treatment interruptions per patient; duration of treatment excluding interruptions relative to the overall follow-up time; frequency of dose change in planned dose by reason as recorded in the eCRF.

The total patient-years while on treatment, calculated as the sum of (overall drug exposure) / 365.25 will be provided by ethnicity group and for all patients.

The average daily dose (planned or actual, in mg/kg) will be calculated as the mean dose over all days between first and last dose, including interim days with zero dose (interruptions). The cumulative dose (planned or actual, in mg/kg) will be calculated as the sum over the daily doses of all days between first and last dose. The current weight of subject will be used when calculating the actual daily dose.

The percentage of planned dose taken will be derived as $100 \times \text{cumulative actual dose (mg/kg)} / \text{cumulative planned dose (mg/kg)}$.

The overall follow-up time will be the number of days between start of study medication and the day before the final visit, both inclusive.

An interruption will be a period of days with a zero actual dose. Only interruptions between start and end of study medication will be taken into account. A patient could have multiple interruptions during the study.

Dose increase and dose reduction will be summarized at week 4, week 24 and approximately every 6 months thereafter. Patient has dose increase at visit if the dose assignment at the visit will be higher than the last available one before the visit. Patient has dose decrease or reduction at visit if the dose assignment at the visit will be nonzero and lower than the last available one before the visit.

Selected efficacy and safety parameters will be summarized by age.

Selected safety data will be summarized by baseline LIC categories

NTDT syndromes or main underlying diseases are Beta-thalassemia intermedia, HbE Betathalassemia, Alpha-thalassemia intermedia (HbH disease) or other. LIC will be summarized by NTDT syndrome.

Selected safety parameters will be summarized by average actual daily dose.

Protocol deviations and patient disposition will be summarized by ethnicity group and listed.

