1.2 Introduction to investigational treatment(s) and other study treatment(s)

To date, deferasirox has been approved in over 100 countries worldwide, including the 28 Member States of the European Union (EU), and the US.

Deferasirox is registered in the following indications:

- For the treatment of chronic iron overload due to blood transfusions (transfusional hemosiderosis) in adult and pediatric patients (aged 2 years and over) at doses up to 40 mg/kg/day.

- For the treatment of chronic iron overload in patients with NTDT syndromes aged 10 years and older with LIC ≥ 5 mg Fe/g d and SF >300 ng/mL at doses of up to 20 mg/kg/day.

Detailed information on preclinical and clinical evaluation of deferasirox is provided in the current [Investigator Brochure].

Deferasirox is formulated as a dispersible tablet for oral suspension which facilitates administration of the appropriate quantity of drug substance to both pediatric and adult patients. Deferasirox is supplied as 125 mg, 250 mg and 500 mg tablets which must be dispersed in water, orange juice or apple juice. A bioavailability study indicates that absorption is highly variable when deferasirox is taken together with food. Therefore, it is recommended that deferasirox is taken once daily, on an empty stomach, at least 30 minutes prior to a meal and no less than 2 hours after the last food intake, consistently at the same time of the day.

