2.5 Rationale for choice of comparators drugs

[figure not shown]
Not applicable

3 Objectives and endpoints

Primary objective

To assess the efficacy of deferasirox in patients with NTDT based on change in LIC from baseline after 52 weeks of treatment.

[figure not shown]
[figure not shown]
Secondary objectives

- Assess response rates in patients with baseline LIC values >15 mg Fe/g dw defined as proportion of patients achieving an LIC <5 mg Fe/g dw and time to achieving LIC <5 mg Fe/g/dw
- Assess long-term efficacy and safety of treatment to target LIC of 3 mg Fe/g dw followed by one or more treatment holidays until the LIC is ≥ 5 mg Fe/g dw
- To evaluate the impact of deferasirox on adult Quality of Life (QoL) using the Medical Outcomes Study Short Form–36 (SF-36) (in patients >18 years of age)
- To evaluate the impact of deferasirox on pediatric QoL using the Pediatric Quality of Life questionnaire (in patients ≤ 18 years of age)
- To evaluate the efficacy of deferasirox based on change in LIC from baseline over time (approximately six month intervals) To assess the correlation of change in SF and LIC at baseline and end of study (EOS)
- To assess the efficacy of deferasirox based on change in LIC from baseline after 52 weeks of treatment by NTDT syndrome
- To assess the efficacy of deferasirox based on change in SF from baseline over time
- To evaluate the safety of deferasirox doses up to 30 mg/kg/day
- To assess the efficacy of deferasirox on endocrine function based on change from baseline over time of the following parameters:
 - Gonad: total and free testosterone (males), luteinizing hormone (LH) and follicle stimulating hormone (FSH) (females)
 - Thyroid: thyroid stimulating hormone (TSH), total and free T4, total and free T3
 - Pancreas: insulin, insulin resistance, fasting plasma glucose (FPG)
 - Adrenal gland: cortisol
- To conduct pharmacokinetic analysis in a subset of patients

Objectives and related endpoints are described in [Table 3-1](#) below.

Table 3-1 Objectives and related endpoints

| Objective | Endpoint | Analysis |
|--|--|--|
| Primary | | |
| Assess the efficacy of deferasirox in liver iron removal after 52 weeks of treatment | Change in LIC from baseline after 52 weeks of treatment | Refer to Section 10.4 |
| Secondary | | |

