1.1 Study design

This open label, single-arm, multi-center study to evaluate the efficacy and safety of deferasirox in NTDT patients with iron overload will include the following phases:

Screening (4 weeks) to determine patient eligibility

Open label treatment with deferasirox:

- Starting dose 10 mg/kg/day for 4 weeks;
- At Week 4, dose adjustments according to baseline LIC:
 - 20 mg/kg/day for patients with baseline LIC > 15 mg Fe/g dw
 - 15 mg/kg/day for patients with baseline LIC > 7 but ≤ 15 mg Fe/g dw
 - Dose will remain at 10 mg/kg/day for patients with baseline LIC ≥ 5 but ≤ 7 mg Fe/g dw
- Approximately every 6 months, starting at Week 24, dose adjustments according to LIC:
 - Increase dose by 5-10 mg/kg/day, if LIC > 15 mg Fe/g dw, maximum of 30 mg/kg/day
 - May increase dose by 5 mg/kg/day if LIC > 7 but ≤ 15 mg Fe/g dw, maximum of 20 mg/kg/day
 - Same dose if LIC is ≥ 3 but ≤ 7 mg Fe/g dw, maximum of 10 mg/kg/day

The maximum dose of deferasirox throughout the study will be 30 mg/kg/day. If LIC measurement is <3 mg Fe/g dw or SF is <300 ng/mL, treatment will be interrupted. Patients who have interrupted study treatment during the first year of the study due to LIC <3 mg Fe/g dw or SF <300 ng/mL will continue the monthly visit schedule. Patients who have treatment interruption due to LIC <3 mg Fe/g dw or SF <300 ng/mL after 52 weeks, will complete scheduled visit one month post-interruption and then be followed every three months.

Study treatment will restart at the previous effective dose when LIC \geq 5 mg Fe/g dw and SF \geq 300 ng/mL (maximum of 10 mg/kg/day). Once on treatment, patients will be followed monthly.

Approximately 117 patients were planned to be enrolled. Treatment duration will be 5 years. Pharmacokinetic analysis was conducted in a subset of 20 patients from selected participating centers.

During the screening phase, patient eligibility was determined, followed by an open-label phase with deferasirox up to five years. Completion of this study occurs after the Last Patient Last Visit of the study, and upon the availability and accuracy verification of the last data point required for final statistical analysis.

No randomization was done in this study. No formal interim analysis based on primary endpoint was planned for this study.

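### The only planned safety-by-dose summary does not separate doses above 20 mg/kg/day, although the safety objective extends to 30

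*SAP*

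**What the plan says.** **Objective.** Protocol Section 3 lists as a secondary objective "To evaluate the safety of deferasirox doses up to 30 mg/kg/day", and SAP Table 1-1 repeats it. Protocol 1.2 describes the registered NTDT indication as LIC of at least 5 mg Fe/g dw and "SF >300 ng/mL at doses of up to 20 mg/kg/day".

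**Route to doses above 20.** From Week 24 the rule in SAP 1.1 is: "Increase dose by 5-10 mg/kg/day, if LIC > 15 mg Fe/g dw, maximum of 30 mg/kg/day". Lower LIC classes are capped at 20 or 10. Treatment is interrupted at LIC below 3 or serum ferritin below 300 ng/mL, and restarted at no more than 10 mg/kg/day. On length, the SAP says "Treatment duration will be 5 years".

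**Safety by dose.** SAP 2.4.1 states: "Selected safety parameters will be summarized by average actual daily dose". The bands are "average actual daily dose (>0 -<7.5, 7.5 - 12.5, >12.5 - 17.5 and >17.5 mg/kg/day"); SAP 2.2.1 lists the same bands as a subgroup. The average is "the mean dose over all days between first and last dose, including interim days with zero dose (interruptions"). Only interruptions that fall between the start and end of study medication count.

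**Other safety summaries.** Under SAP 2.1 and 2.7, adverse events, laboratory values, vital signs and gastrointestinal events are summarised by ethnicity group and overall. None of these is split by dose at onset, maximum dose or time at a dose. SAP 2.4.1 also plans selected safety data by baseline LIC category.

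**The concern.** What this objective adds to the registered use is the range above 20 mg/kg/day. Protocol 1.2.1.2 describes the gastrointestinal, rash and creatinine effects of deferasirox as dose-dependent, so a reader will look for them there. The dose grouping has three features that work against this.

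1. The open top band pools patients never assigned more than 20 with patients at 25 to 30.
2. The average runs over the patient's whole treatment span, with zero-dose days inside that span counted. Later step-downs and interruptions can therefore move a patient with long exposure at 30 into a lower band.
3. The grouping variable is affected by the outcome. Confirmed creatinine rises (Protocol 6.4.4), rash (6.4.7) and hepatic impairment (6.4.9) lead to dose reduction or interruption. These lower the average under which the triggering event is later tabulated.

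The second and third features tend to flatten any relation between dose and toxicity in the table. The first leaves no category in which the range above 20 can be read.

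**Working it through.** The plan states no figure to reproduce. The check applies the SAP's definition to assumed dose paths built from the protocol's dose steps.

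**Formula.** Average = sum of (weeks × dose) / weeks from first to last dose, then allocation to the SAP 2.4.1 bands. The longest window is 260 weeks.

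**1. What the top band pools**
- 4 weeks at 10, then 256 at 20: (40 + 5120)/260 = 19.85, band >17.5. Never above 20.
- 4 weeks at 10, 20 at 20, 236 at 30: (40 + 400 + 7080)/260 = 28.92, band >17.5. Above 20 for 236 weeks.

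**2. Long exposure at 30 in a lower band**
- 4 weeks at 10, 20 at 20, 28 at 25, 52 at 30, 52 at 20, 78 off, 26 at 10: (40 + 400 + 700 + 1560 + 1040 + 0 + 260)/260 = 4000/260 = 15.38, band >12.5 to 17.5. Over the 182 non-zero weeks, 4000/182 = 21.98.
- 4 weeks at 10, 20 at 20, 104 at 30, 28 at 10, 52 off, 52 at 10: (40 + 400 + 3120 + 280 + 0 + 520)/260 = 16.77, the same band despite two years at 30.
- No interruption at all: 4 weeks at 10, 20 at 20, *w* weeks at 30 and the rest at 10. At *w* = 87 the average is (440 + 2610 + 1490)/260 = 17.46; at 88 it is 4560/260 = 17.54. Up to 87 weeks at 30 can thus fall below the top band. With a 52-week interruption the limit is 113 weeks: (440 + 3390 + 710)/260 = 17.46.

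**3. Dependence on later restart**
- 4 weeks at 10, 20 at 20, 52 at 30, 52 at 20, 28 at 10, then 52 off and 52 at 10: 3840/260 = 14.77, band >12.5 to 17.5.
- The same history, never restarted: 3320/156 = 21.28, band >17.5.

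Two patients with identical dosing up to Week 156 are placed in different bands by what happens afterwards.

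**4. A cut caused by toxicity**
- Protocol 6.4.4 takes a patient from 30 to 15 after a confirmed creatinine rise. Assume 4 weeks at 10, 20 at 20, 28 at 30, then 15 for the remaining 208 weeks: (40 + 400 + 840 + 3120)/260 = 16.92. The creatinine event that arose at 30 is tabulated under >12.5 to 17.5.

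**5. Which dose variable separates the classes**
- Doses are rounded to 125 mg. In Protocol Table 6-4 (assigned 20), 1000 mg at 47.0 kg is 21.3 mg/kg and 500 mg at 22.0 kg is 22.7 mg/kg. In Table 6-5 (assigned 25), 500 mg at 22.5 kg is 22.2 mg/kg.
- A cut at 20 on actual dose would admit patients never assigned more than 20, and a cut at 22.5 still misplaces some of the lightest patients.
- Dropping zero-dose days and splitting the top band at 22.5 is not enough either: the first path in step 2 averages 21.98 and stays below that cut despite a year at 30.

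**The case against.** **The objective is narrower than it looks.** It can be read as the safety of an LIC-titrated regimen capped at 30, which the overall Safety Set tables describe. Protocol 10.5.10 promises no dose strata. This stands against any claim that the objective cannot be addressed at all. It does not supply a description of safety above 20.

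**Baseline LIC is a useful proxy.** Doses above 20 require LIC above 15, and baseline LIC is fixed before treatment, so toxicity cannot move patients between its classes. This stands in part. The class above 15 still mixes patients who went above 20 with those who responded at 20.

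**The example paths are selective.** The path averaging 15.38 needs high LIC for about two years, then a fall to the interruption threshold, a 78-week interruption and a restart. Protocol 1.2.1.2 reports that about 16% reached LIC below 3 within up to two years in the companion study, so interruptions may be less common among patients who reach 30. This stands as to frequency. The pooled top band needs no interruption, and step-down alone can also lower the band.

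**The lower bands are inherited.** They match those reported for the companion study, and Protocol Section 10 favours consistency with it. But dosing there rose only to 20, so the bands were not built for a study that reaches 30.

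**Dose at onset is not unbiased.** Escalation follows iron burden and earlier tolerability (Protocol 2.3). This stands, and the tables should say so.

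**Stronger readings the documents do not support.** A reader might infer that no output of any kind could show events above 20. The selected parameters are not itemised, no table shells are public, SAP Section 2.9 does not appear in the public text, and patient listings would allow a later reconstruction. A reader might also infer that every event at 25 to 30 is tabulated in a lower band, or that the average always covers five years. Patients who stay at 25 to 30 fall in the top band. The window ends at the last dose, so it is shorter for patients who discontinue and leaves out a final interruption without restart.

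**Conclusion.** The point holds in this form: the planned summaries in the public text do not separately describe safety above 20 mg/kg/day. Pooling in the top band follows directly from the definitions (19.85 and 28.92 in one class). Movement into lower bands is possible, not general: it can occur with up to 87 weeks at 30 without any interruption, and up to 113 weeks with one of 52 weeks, when all remaining weeks after the first 24 are at 10.

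All dose paths are assumptions. The documents give no number of patients or person-years above 20, so neither the frequency of misplacement nor the precision of a better table can be computed. The primary LIC result is unaffected. The change is worth making because a named safety objective covers this range and the planned dose table cannot isolate it.

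**What to change.** Add to SAP 2.7 tables of treatment-emergent adverse events and of notable renal and liver values by **assigned (planned) dose at onset**, with a separate class for assigned dose above 20 (25 to 30) mg/kg/day and person-time in each class as denominator. Use assigned dose because 125 mg rounding puts some patients assigned 20 above 20 in actual dose.

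Two rules should be set in advance:
- How events that start during an interruption are classed.
- That abnormalities requiring two consecutive measurements take the dose at the first, so that the resulting dose cut does not reclassify them.

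Keep the average-dose table as descriptive. State beside the new tables that dose at onset depends on iron burden and prior tolerability, so that they are not read as a causal dose-response.

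Cost: a few more tables from dosing records the study already collects, and no change to conduct. Some cells may be small; counts with person-time remain informative there.

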4.1 Description of study design

This open label, single-arm, multi-center study to evaluate the efficacy and safety of deferasirox in NTDT patients with iron overload will include the following phases:

Screening (4 weeks) to determine patient eligibility

Open label treatment with deferasirox:

- Starting dose 10 mg/kg/day for 4 weeks;
- At Week 4, dose adjustments according to baseline LIC:
 - 20 mg/kg/day for patients with baseline LIC > 15 mg Fe/g dw
 - 15 mg/kg/day for patients with baseline LIC > 7 but ≤ 15 mg Fe/g dw
 - Dose will remain at 10 mg/kg/day for patients with baseline LIC ≥ 5 but ≤ 7 mg Fe/g dw
- Approximately every 6 months, starting at Week 24, dose adjustments according to LIC:
 - Increase dose by 5-10 mg/kg/day, if LIC > 15 mg Fe/g dw, maximum of 30 mg/kg/day
 - May increase dose by 5 mg/kg/day if LIC >7 but ≤ 15 mg Fe/g dw, maximum of 20 mg/kg/day
 - Same dose if LIC is ≥3 but ≤ 7 mg Fe/g dw, maximum of 10 mg/kg/day

The maximum dose of deferasirox throughout the study will be 30 mg/kg/day.

If LIC measurement is <3 mg Fe/g dw or SF is <300 ng/mL, treatment will be interrupted. Patients who have interrupted study treatment during the first year of the study due to LIC <3 mg Fe/g dw or SF <300 ng/mL will continue the monthly visit schedule. Patients who have treatment interruption due to LIC <3 mg Fe/g dw or SF <300 ng/mL after 52 weeks, will complete scheduled visit one month post-interruption and then be followed every three months.

Study treatment will restart at the previous effective dose when LIC ≥5 mg Fe/g dw and SF ≥ 300 ng/mL (maximum of 10 mg/kg/day). Once on treatment, patients will be followed monthly.

See [Figure 4-1](#), for study design schematic.

[figure not shown]
[figure not shown]

Figure 4-1 Study Design

Approximately 117 patients will be enrolled. Treatment duration will be five years. Pharmacokinetic analysis will be conducted in a subset of 20 patients from selected participating centers.

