7.2 Assessment types

7.2.1 Efficacy assessments

7.2.1.1 Liver iron content (LIC) assessment by MRI

[figure not shown]
Change in LIC from baseline after 52 weeks of treatment with study drug will be used as primary efficacy parameter. And, change in LIC from baseline after approximately six month intervals of treatment with study drug will be used as a secondary efficacy parameter.

LIC will be measured at Screening Visits 1 or 2, Visit 15 (week 24), Visit 25 (week 52), and approximately every six months thereafter (weeks 76, 104, 128, 156, 180, 208, 232, and 260) using a validated R2 MRI technique. All patients enrolled in the study will have MRI scans using a specific sequence. Raw image data will be analyzed centrally to determine the patient's LIC value. The result of the measurement will be provided to the sites by the central laboratory.

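### The SAP's dose-increase rule does not exclude a zero assignment as comparator, so a restart after an interruption can be tabulated as an increase when the dose is unchanged or lower

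*SAP*

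**What the plan says.** SAP 2.4.1 sets the visits for the table: "Dose increase and dose reduction will be summarized at week 4, week 24 and approximately every 6 months thereafter". For an increase, the requirement is that the "dose assignment at the visit will be higher than the last available one before the visit". For a reduction, the requirement is that the "dose assignment at the visit will be nonzero and lower than the last available one before the visit". The section gives no rule for a restart and does not define 'last available'.

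Interruptions and restarts are part of the design. SAP 1.1 states: "If LIC measurement is <3 mg Fe/g dw or SF is <300 ng/mL, treatment will be interrupted". Protocol 4.1 says: "Study treatment will restart at the previous effective dose when LIC" is at least 5 mg Fe/g dw and serum ferritin is at least 300 ng/mL, with a stated maximum of 10 mg/kg/day. The same maximum appears in SAP 1.1 and Protocol 6.4.2. Before an interruption a patient may be on more than that. From Week 4 the assignment is 15 or 20 mg/kg/day when baseline LIC is above 7 or above 15, and later adjustments may go up to 30 (Protocol 4.1 and 6.1.1).

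**The concern.** The two rules are not symmetric. The reduction rule needs the word 'nonzero' only if zero assignments are expected in the data, and its effect is that the start of an interruption is not called a reduction. The increase rule has no matching condition on the comparator, so coming back from zero to any dose meets it.

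This SAP supports the final report, and treatment to target followed by holidays is one of the study's secondary objectives. The table is meant to show when doses went up and when they went down. If restarts are counted among the increases, a reader cannot separate escalation for high liver iron from resumption after an interruption. For a patient who restarts below the last dose taken, the table shows the opposite of what happened. Because 'last available' is undefined, two programmers could also classify the same record in opposite ways.

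**Working it through.** The plan gives no figure to reproduce. The check applies the two rules as written to dose sequences.

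Let *a* be the assignment at a tabulated visit and *b* the last available assignment before it.

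- Increase: a > b.
- Reduction: a ≠ 0 and a < b.
- Otherwise: neither.

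Doses are in mg/kg/day. The last column replaces *b* by the last nonzero assignment.

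| Sequence | Step to zero, as written | Restart, as written | Restart against last nonzero dose |
|---|---|---|---|
| 20→0→10 | a = 0, neither | 10 > 0, increase | 10 < 20, reduction |
| 15→0→10 | neither | 10 > 0, increase | 10 < 15, reduction |
| 30→0→10 | neither | 10 > 0, increase | 10 < 30, reduction |
| 10→0→10 | neither | 10 > 0, increase | 10 = 10, no change |
| 10→0→5 | neither | 5 > 0, increase | 5 < 10, reduction |
| 20→10→0→10 | neither | 10 > 0, increase | 10 = 10, no change |

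In the last row the earlier step from 20 to 10 is counted as a reduction (10 < 20), and the restart is still counted as an increase. The fifth row is the kind of sequence that can follow a safety interruption, since Protocol 6.4.4 and 6.4.7 both describe resuming at a reduced dose.

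Timing decides whether the effect appears. If the restart to 10 happens between tabulated visits and the dose is still 10 at the next one, then a = 10 and b = 10, and the restart is counted as neither. With a zero comparator, a restart is never counted as a reduction.

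Restarts at tabulated visits are plausible. Protocol 7.2.1.1 schedules LIC at Weeks 24, 52, 76 and so on, the same rhythm as the table, and Table 7-1 marks dose adjustment at Week 4 and at those visits. They are not assured. LIC is read centrally ("Raw image data will be analyzed centrally to determine the patient's LIC value"), and Protocol 6.4.2 has a low ferritin prompt its own MRI and a repeat ferritin within two weeks, so some stops and restarts will be off schedule.

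**The case against.** **The zero comparator is inferred.** SAP 2.4.1 defines an interruption as a period of zero actual dose, while the increase rule compares assignments. The section does include zero-dose days when averaging planned or actual dose ("including interim days with zero dose (interruptions"), and 'nonzero' would be idle if zero assignments never occurred. Still, nothing says that a holiday is stored as a zero assignment or that a zero counts as available. If 'available' meant the last nonzero dose, the problem would disappear. This stands, and it is why the point is conditional.

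**A reversed direction may be uncommon.** The documents state a maximum of 10 mg/kg/day at LIC 3 to 7, so a patient scanned in that band before falling below 3 may already be at 10 or less, with the step-down counted. Going straight from 20 to zero needs LIC to fall from above 7 to below 3 between scans, a ferritin trigger, or a safety interruption. This stands as a limit. The restart from such a path (10→0→10) is still counted as an increase.

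**Other summaries overlap.** SAP 2.4.1 also plans the number and length of interruptions and the frequency of planned-dose changes by reason. Protocol 10.3 adds frequency tables and a listing of adjustments with reasons. These help a reader separate restarts from escalations, but they do not correct the direction shown in this table.

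**Two stronger readings are tempting and not supported.** A reader might take the 16% of patients who reached LIC below 3 within 2 years in the earlier trial (Protocol 1.2.1.2) and compute 0.16 × 134 = 21.4 as the number misclassified. That figure estimates entries into a holiday, not restarts, and not restarts at a tabulated visit. The Amendment 1 rationale says that the earlier trial was too short for such patients to re-accumulate enough iron to need re-treatment. A reader might also infer that true escalations are missed because central MRI results arrive after the visit. The documents give no turnaround time. The same delay would also keep LIC-dependent restarts out of the table, so this inference works against the main point.

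**Conclusion.** The point holds on the plain wording, on the assumption that interruptions are recorded as zero assignments. A restart that is the assignment at a tabulated visit is then counted as an increase even when the dose is the same as, or lower than, the last nonzero dose. A restart between tabulated visits is counted as neither.

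The number affected cannot be derived. It would need the number of restarts, the share that coincide with tabulated visits, and the last dose before each interruption, none of which the documents give. It should not be read as saying that every holiday produces a false increase.

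The consequence is limited to one descriptive exposure table. The primary analysis, the secondary endpoints, the safety rates and all tests are untouched. It is still worth acting on: in a study built around holidays and restarts, the stated rule gives a wrong classification, and the remedy is specific and cheap.

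**What to change.** In SAP 2.4.1, define both increase and reduction by comparing each nonzero assignment with the last nonzero assignment. Tabulate interruptions (nonzero to zero) and restarts (zero to nonzero) as their own categories, showing each restart dose against the last nonzero dose. State explicitly how an interruption is represented in the assignment data.

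The cost is a change of SAP wording and one derivation. No new data are needed, because all prescribed doses and dose changes go on the Dosage Administration Record (Protocol 6.1.1). The number of reported increases will be smaller, and some restarts will appear as lower than the previous dose.
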